2.9.1.4 Adverse events of special interests

An adverse event of special interest (AESI) is a grouping of AEs that are of scientific and medical concern specific to Capmatinib. These grouping are defined using MedDRA terms, SMQs (standardized MedDRA queries), HGLTs (high level group terms), HLT (high level terms) and PTs (preferred terms). Customized SMQs (Novartis MedDRA queries, NMQ) may also be used. A NMQ is a customized group of search terms which defines a medical concept for which there is no official SMQ available or the available SMQ does not completely fit the need. It may include a combination of single terms and/or an existing SMQ, narrow or broad. For each specified AESI, the number and percentage of subjects with at least one event of AESI occurring during on-treatment period will be summarized:

- Overview of adverse events of special interest for Capmatinib

A listing of all grouping levels down to the MedDRA preferred terms used to define each AESI will be generated.

Note: From the eCSR, only risk where “Core Safety Risk” = Y should be selected to report Adverse events of special interest in the CSR (the available name in GPS, for “Core Safety Risk”, is SP).

2.9.1.5 Death

On-treatment deaths will be produced by study treatment group, SOC and PT. All deaths will be listed using safety set, post treatment deaths will be flagged.

2.9.1.6 Imputation rules for missing AE date

A missing AE start date will be imputed using the following logic matrix described in [Table 2-3](#).

Table 2-3 Imputation rules for a partially missing AE start date

	AEM MISSING	AEM < TRTM	AEM = TRTM	AEM > TRTM
AEY MISSING	No imputation	No imputation	No imputation	No imputation
AEY < TRTY	(D)	(C)	(C)	(C)
AEY = TRTY	(B)	(C)	(B)	(A)
AEY > TRTY	(E)	(A)	(A)	(A)

AEM: Month AE started; AEY: Year AE started

TRTM: Month treatment started; TRTY: Year treatment started

[Table 2-4](#) is the legend to the logic matrix shown in [Table 2-3](#) and details the relationship of AE start date to study treatment start date.

Table 2-4 Imputation legend and AE/treatment start date relationship

AE start date relationship	Imputation
(A) After treatment start or Uncertain	MAX(01MONYYYY, TRTSTD+1)
(B) Uncertain	TRTSTD+1
(C) Before treatment start	15MONYYYY
(D) Before treatment start	01JULYYYY
(E) After treatment start	01JANYYYY

Before treatment start: Partial date indicates AE start date is prior to treatment start date.

After treatment start: Partial date indicates AE start date is after treatment start date.

Uncertain: Partial date insufficient to determine relationship of AE start date to treatment start date.

No imputation will be performed for AE end dates.

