The occurrence of AEs should be sought by non-directive questioning of the patient (subject) during the screening process after signing informed consent and at each visit during the study. AEs also may be detected when they are volunteered by the patient (subject) during the screening process or between visits, or through physical examination, laboratory test, or other assessments. As far as possible, each AE should be evaluated to determine:

1. The severity Grade (CTCAE Grade 1-4)
2. Its duration (Start and end dates)
3. Its relationship to the study treatment (Reasonable possibility that AE is related: No, Yes)
4. Action taken with respect to study or investigational treatment (none, dose adjusted, temporarily interrupted, permanently discontinued, unknown, not applicable)
5. Whether medication or therapy was given (no concomitant medication/non-drug therapy, concomitant medication/non-drug therapy)
6. Outcome (not recovered/not resolved, recovered/resolved, recovering/resolving, recovered/resolved with sequelae, fatal, unknown)
7. Whether it is serious, where a SAE is defined as in [Section 8.2.1](#), and which seriousness criteria have been met.

All AEs should be treated appropriately. If a concomitant medication or non-drug therapy is given, this action should be recorded on the AE CRF.

Once an AE is detected, it should be followed until its resolution or until it is judged to be permanent, and assessment should be made at each visit (or more frequently, if necessary) of

any changes in severity, the suspected relationship to the study treatment, the interventions required to treat it, and the outcome.

Progression of malignancy (including fatal outcomes), if documented by use of appropriate method (for example, as per RECIST criteria for solid tumors), should not be reported as a SAE.

AEs separate from the progression of malignancy (example, deep vein thrombosis at the time of progression or hemoptysis concurrent with finding of disease progression) will be reported as per usual guidelines used for such events with proper attribution regarding relatedness to the drug.

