1. ***pre-treatment period:*** from day of patient’s first informed consent to the day before first administration of study treatment
2. ***on-treatment period:*** from date of first administration of study treatment to 30 days after date of last actual administration of any study treatment (including start and stop date)
3. ***post-treatment period:*** starting at day 30+1 after last administration of study treatment.

Safety summaries include only data from the on-treatment period with the exception of baseline data which will also be summarized where appropriate (e.g. change from baseline summaries). In particular, summary tables for adverse events (AEs) will summarize only on-treatment events, with a start date during the on-treatment period (**treatment-emergent** AEs).

However, all safety AE data (including those from the pre-treatment period) will be listed.

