2.9.1.3 AE summaries

AE summaries will include all AEs occurring during on-treatment period (Section 2.1.1). All AEs collected in the AE (e)CRF page will be listed along with the information collected on those AEs e.g. AE relationship to study drug, AE outcome etc. AEs starting during the post-treatment period will be flagged in the listings.

AEs will be summarized by number and percentage of patients having at least one AE, having at least one AE in each primary system organ class (SOC) and for each preferred term (PT) using MedDRA coding. A patient with multiple occurrences of an AE will be counted only

once in the respective AE category. A patient with multiple CTCAE grades for the same preferred term will be summarized under the maximum CTCAE grade recorded for the event. AE with missing CTCAE grade will be included in the 'All grades' column of the summary tables.

In AE summaries the SOC will be presented alphabetically and the PTs will be sorted within primary SOC in descending frequency, based on their frequency in the 'All Patients' column.

The following AE summaries will be produced by study treatment group:

- Overview of AE
- AEs regardless of study treatment relationship by SOC, PT and maximum grade
- AEs regardless of study treatment relationship by PT and maximum grade
- AEs suspected to be study treatment related by PT and maximum grade
- SAEs regardless of relationship to study treatment by PT and maximum grade
- SAEs suspected to be study treatment related by PT and maximum grade
- Summary of qualifying AE for dose decision analysis (Dose determining part only)
- AEs leading to discontinuation of study treatment regardless of relationship to study treatment by PT and maximum grade
- AEs leading to discontinuation of study treatment suspected to be study treatment related by PT and maximum grade
- AEs requiring dose adjustment/interruption by SOC, PT and maximum grade
- AEs requiring additional therapy by SOC, PT and maximum grade

Additionally, for the legal requirements of ClinicalTrials.gov and EudraCT, two required tables on on-treatment adverse events which are not serious adverse events with an incidence greater than 5% and on on-treatment serious adverse events and SAE suspected to be related to study treatment will be provided by system organ class and preferred term on the safety set population.

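### Read together, SAP Table 2-3 and SAP 2.1.1 leave an adverse event with no start year out of the AE tables: probably rare, but where it errs it only lowers counts

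*SAP*

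**What the plan says.** The lead-in to SAP 2.9.1.6 promises a general rule: "A missing AE start date will be imputed using the following logic matrix described in" Table 2-3. The first row of that table then reads "AEY MISSING No imputation No imputation No imputation No imputation". The other three rows, where the start year is known, assign one of the categories (A) to (E), and each of these returns a date. The Table 2-4 legend explains the label used for (B): "Uncertain: Partial date insufficient to determine relationship of AE start date to treatment start date". Under (B) the start is set to the day after first dose.

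SAP 2.1.1 sets the entry condition for AE tables: "summary tables for adverse events (AEs) will summarize only on-treatment events, with a start date during the on-treatment period". The period runs "from date of first administration of study treatment to 30 days after date of last actual administration of any study treatment". SAP 2.9.1.3 repeats the restriction ("AE summaries will include all AEs occurring during on-treatment period (Section 2.1.1") and lists the tables under it. These include the SAE tables, the tables of AEs requiring dose adjustment or additional therapy, and "AEs leading to discontinuation of study treatment regardless of relationship to study treatment by PT and maximum grade". The registry tables in the same section, and the table of AEs of special interest in SAP 2.9.1.4, are also limited to on-treatment events. SAP 2.1.1 adds that all AE data are listed whatever the period.

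Protocol 10.5.3.2 commits to summarizing every AE recorded during the study.

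**The concern.** The two SAP rules do different jobs, but together they decide whether an event is counted. A record without a start year gets no date under Table 2-3, and a record without a date cannot satisfy a condition framed in terms of a start date. The event is then missing from the AE tables for lack of a date, not because anything shows that it fell outside the on-treatment period.

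That sits badly with the rest of the table. Where the year is known but the relation to first dose is uncertain, the SAP takes the cautious course and counts the event. Where still less is known, it does the opposite. The event's own record may settle the matter: Protocol 8.1.1 collects, for each AE, "Action taken with respect to study or investigational treatment", as well as relatedness to study treatment. An AE recorded as having led to permanent discontinuation can be relevant to the on-treatment tables without any start date, but the SAP makes no use of this.

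What is at stake is a possible small under-count in the safety tables. Where the rule is wrong, it is wrong in the reassuring direction.

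**Working it through.** The plan states no figure to reproduce. The check is of the rules, followed by simple arithmetic for size.

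**Step 1: cells of Table 2-3.** Four rows (year missing, before, equal to, after the treatment-start year) by four columns (month missing, before, equal to, after the treatment-start month) give 16 cells. The four with a missing year return no date; the other 12 do.

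**Step 2: apply the SAP 2.1.1 test.** I assume, for illustration, a first dose on 15-Jan-2014 and a last dose on 30-Jun-2014. The on-treatment period then ends 30 days later, on 30-Jul-2014.

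| Recorded AE start | Category | Imputed start | On-treatment? |
|---|---|---|---|
| Year and month missing | none | none | no date, test fails |
| Year missing, January | none | none | no date, test fails |
| Year missing, March | none | none | no date, test fails |
| 2014, month missing | (B) | 16-Jan-2014 | yes |
| January 2014 | (B) | 16-Jan-2014 | yes |
| March 2014 | (A) | 1-Mar-2014 | yes |
| 2013, month missing | (D) | 1-Jul-2013 | no |
| December 2013 | (C) | 15-Dec-2013 | no |

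With a known year, an event is excluded here only when the partial date shows that it began before treatment. With an unknown year it is excluded by default.

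**Step 3: look for a rule that rescues the record.**
- SAP 4.1 deals with end dates only.
- SAP 2.9.1.3 keeps an AE with a missing grade in the all-grades column, but has no counterpart for a missing year.
- SAP section 4 names only the per-protocol analysis as a change from the protocol, so a departure from Protocol 10.5.3.2 is not declared.

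**Step 4: where such an event most likely belongs.** Under Protocol 8.1.1, conditions present at consent go to medical history and the AE page holds what begins or worsens afterwards. Protocol 4.1 has treatment start within 14 days of the beginning of screening assessments. AE monitoring runs for at least 30 days after last dose, and the on-treatment period also ends 30 days after last dose. The time outside the period in which an AE would routinely be recorded is therefore short, though not zero.

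**Step 5: size.** Protocol 1.2.1.2.2 gives 8 patients at 300 mg bid and 28 in the expansion part at 28 September 2015. If one patient is lost from a table row:
- 300 mg bid: 1/8 = 12.5 percentage points
- Expansion part: 1/28 = 3.6 percentage points

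In a group of 28, a non-serious term that falls from 2 patients (2/28 = 7.1%) to 1 (1/28 = 3.6%) would drop out of the registry table, whose threshold is above 5%.

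**The case against.** **No sentence says that undated AEs are excluded.** True: the exclusion follows from reading two rules together. Variable derivations sit in a separate programming specification, which might set a treatment-emergent flag for such records. That is possible, but the SAP as written gives a condition that these records cannot meet, and a different rule belongs in the SAP.

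**The case may hardly ever arise.** Protocol 8.1.1 asks for start and end dates for each AE and has AEs sought at every visit. Protocol 9.4 has missing values queried, and Protocol 8.2.2 requires SAEs to be reported within 24 hours of awareness. An SAE whose year cannot be established is hard to picture. This stands, and it is why the point is minor.

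**Category (B) is anchored to a known year.** With no year the event could be pre-, on- or post-treatment, so declining to invent a date is a defensible choice. This stands in part. It argues for exceptions on both sides when the event is counted, not for leaving it out by default.

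**A reader might infer that the event disappears from the report.** The documents do not support that. It remains in the listings. Discontinuations and their reasons are summarized from the end-of-treatment page (SAP 2.3.1) and the dosing page (SAP 2.5.2.4), laboratory abnormalities from laboratory values (SAP 2.9.2), and on-treatment deaths separately (SAP 2.9.1.5). Only the AE tables lose it.

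**A reader might also infer that each lost record shifts incidence by 12.5 or 3.6 points.** SAP 2.9.1.3 counts a patient once per category, so the shift is zero if the patient has another tabulated record of the term. The 28 is an interim count: enrolment was halted only in December 2016, and SAP 2.1 reports safety by dose and formulation, with a separate 400 mg tablet group.

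**Conclusion.** The rules are wrong as written, and the consequence is minor. Taken together, SAP Table 2-3 and SAP 2.1.1 leave an AE with a missing start year out of the AE tables, including those for SAEs, AEs leading to discontinuation and AEs of special interest. This runs against the SAP's own treatment of uncertain timing in Table 2-4 and against Protocol 10.5.3.2.

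The figures in the working are upper limits for one record: one patient per term, and only where it is that patient's sole record of the term. The number of such records is not given, and no effect on any result of this trial is shown. The conclusion assumes that no document outside the protocol and SAP sets a different default.

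**What to change.** In SAP 2.1.1 and Table 2-3, count an AE with a missing start year as treatment-emergent: assign category (B), the day after first dose, and flag the imputed date in the listing. Make an exception where the recorded end date, or other recorded data, show that the event began before first dose or more than 30 days after last dose. The second half of the exception matters, because a bare switch to (B) would place a late post-treatment event on Day 2.

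The cost is one table row and one sentence, made by SAP amendment before database lock or by addendum after it. No new data are needed. The downside is that an occasional pre- or post-treatment AE of unknown year may be counted as on-treatment. That is the conservative direction, and category (B) already accepts it for other uncertain dates.

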4.1 Handling of missing and partial dates

For patients not known to have died prior to the cut-off date:

All events (e.g. AEs) that started before or on the cut-off date, and with end date missing or after the cut-off date will be reported as continuing and unresolved at the cut-off date. For these events, the end date will not be imputed.

Calculating duration of e.g. AEs and concomitant medications for patients known to have died prior to or on the cut-off date:

AEs and concomitant medications that started before or on the cut-off date, and with end date missing or after the cut-off date will have the end date imputed to the date of death. For these events, the imputed end date will not appear in the listings.

If imputation of an end date is required to calculate the duration of exposure to study treatment (a dose administration record with missing end date, or last date of study treatment is after the cut-off date), the end date will be imputed to the cut-off date. The imputed date will be displayed and flagged in the listings.

5 References

Cheng AL, et al (2009) Efficacy and safety of sorafenib in patients in the Asia-Pacific region with advanced hepatocellular carcinoma: a phase III randomized, double-blind, placebo controlled trial. *Lancet Oncol* 10:25–34

Santoro A, et al (2013). Tivantinib for second-line treatment of advanced hepatocellular carcinoma: a randomised, placebo-controlled phase 2 study. *Lancet Oncol* 14: 55Onc

Neuenschwander, Branson, Gsponer (2008) Critical aspects of the Bayesian approach to Phase I cancer trials. *Statistics in Medicine*, 27:2420-2439.

Neuenschwander B, Capcun–Niggli G, Branson M et al (2010) Summarizing Historical Information on Controls in Clinical Trials. *Clin Trials*; 7(1): 5-18.Clopper CJ and Pearson ES (1934). The Use of Confidence or Fiducial Limits Illustrated in the Case of the Binomial. *Biometrika*; 26,(4):404-13.

Kaplan, EL and Meier, P (1958). Nonparametric estimation from incomplete observations. *Journal of the American Statistical Association*;53:457-81.

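### The SAP imputes a partial AE start date without looking at a recorded end date, so an AE known to have ended before first dose can be counted as treatment-emergent

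*SAP*

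**What the plan says.** SAP 2.9.1.6 imputes a partial AE start date from a grid (Table 2-3) with a legend (Table 2-4). The AE inputs to the grid are "AEM: Month AE started; AEY: Year AE started", compared with the month and year of treatment start. Cell (B) applies when the AE year equals the treatment-start year and the AE month is the same or missing. Its legend entry is "B) Uncertain TRTSTD+1", that is, the day after first dose. The term is explained as "Uncertain: Partial date insufficient to determine relationship of AE start date to treatment start date", so uncertainty is judged on the partial start date alone.

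The AE end date appears in that section only once: "No imputation will be performed for AE end dates".

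SAP 2.1.1 then decides which events reach the tables: "summary tables for adverse events (AEs) will summarize only on-treatment events, with a start date during the on-treatment period". The on-treatment period runs "from date of first administration of study treatment to 30 days after date of last actual administration of any study treatment", so the day after first dose lies inside it.

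SAP 4.1 has a separate rule on AE end dates for patients known to have died by the cut-off: AEs "with end date missing or after the cut-off date will have the end date imputed to the date of death". That rule stands under a lead-in about calculating durations.

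**The concern.** Setting an unknown start to the day after first dose is a sensible cautious choice when the order of AE onset and first dose cannot be established. It stops being sensible when the record itself shows that the AE was over before any INC280 was taken. The grid cannot see this, because the end date is not one of its inputs.

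Such records can occur. Protocol 8.1.1 has AEs recorded from main informed consent and asks for both start and end dates, and Protocol 4.1 allows up to 14 days between the start of screening assessments and first dose. An AE that came and went in screening is therefore in the database, and if its start date is incomplete the rule can move it into the on-treatment period. At stake is the accuracy of the treatment-emergent AE tables, together with an impossible date order in the derived data.

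**Working it through.** The plan gives no figure for this rule, so there is none to reproduce. The check codes Tables 2-3 and 2-4 and the study-day formula of SAP 2.1.1 as written. The coded formula returns the SAP's own two study-day examples, 5 and -3.

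**One record.** Assumed dates: first dose 20-Jan-2014, AE end 15-Jan-2014. Duration = end - start + 1.

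| Recorded start | Cell | Imputed start | Study day | Duration (days) | Treatment-emergent? |
|---|---|---|---|---|---|
| Jan-2014 | B | 21-Jan-2014 | 2 | 15 - 21 + 1 = -5 | Yes |
| 2014 only | B | 21-Jan-2014 | 2 | -5 | Yes |
| Dec-2013 | C | 15-Dec-2013 | -36 | 32 | No |
| 2013 only | D | 01-Jul-2013 | -203 | 199 | No |

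In the first two rows the AE starts 6 days after it ended. The last two rows show that cells (C) and (D) keep the AE in the pre-treatment period. Cells (A) and (E) need a start month or year after that of treatment start, which cannot go with an end before first dose unless the data are wrong. The fault is therefore confined to cell (B).

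**How often the pattern falls in cell (B).** Take every first-dose date from 01-Jan-2014 to 25-Dec-2016 (an assumed range of 1,090 days) and every AE that starts and ends on days -14 to -1. Each first-dose date has 14 × 15 / 2 = 105 start/end pairs, so there are 1,090 × 105 = 114,450 patterns.

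- Day missing: 68.1% fall in cell (B).
- Day and month missing: 97.3% fall in cell (B).

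Every one of these gets a start after its own end and becomes treatment-emergent.

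A hand check agrees. An AE starting k days before first dose has k possible end days, so the average lead weighted over pairs is (sum of k²) / (sum of k) = 1,015 / 105 = 9.67 days. With an average month of 365.25 / 12 = 30.44 days, the chance of the same calendar month is about 1 - 9.67 / 30.44 = 0.68. The chance of the same year is about 1 - 9.67 / 365 = 0.97.

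**After the fix.** If the start is capped at an end date that precedes first dose, the example moves to 15-Jan-2014 at the latest (study day -5, pre-treatment). Both percentages fall to 0.

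**Comparison within the SAP.** SAP 2.5.1.1, on imputing the last dosing date, compares the imputed date with the start date of the same record and corrects an impossible order. No such check is stated for AEs.

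**The case against.** The best defence is that the effect is small and leans the safe way. Much of that stands. The fault needs a partial start date, in cell (B), with an end date known to precede first dose. AEs are sought at each visit and missing values are queried (Protocol 8.1.1 and 9.4), which should make such records uncommon. SAP 2.9.1.3 counts a patient once per term, so a misplaced record adds at most one patient to a term. An AE that was over before any drug was taken should not appear as drug-related or as a cause of discontinuation, and qualifying AEs must be judged related (Protocol 6.2.3), so the dose decision should be untouched. Any bias over-counts on-treatment events, and all AEs are listed whatever their period. None of this makes the classification right where the end date already settles the order.

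The Programming Datasets Specifications were not available and may contain a date check. The SAP states its AE rule in full and points to no such exception.

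Three stronger readings might be inferred, and the documents do not support them:

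- That the imputation to date of death in SAP 4.1 stretches a resolved AE with a missing end date until death, and so merges later episodes of the same term under the one-day-gap rule of SAP 2.9.1.3. The 4.1 rule is for calculating duration, and no text carries it into the occurrence count. What remains is that 2.9.1.6 states its no-imputation sentence without mentioning the 4.1 exception.
- That a first dose on the last day of a month creates a further error, because the next day lies outside the recorded AE month. First-dose day is itself on-treatment, so moving the start back to it changes no classification.
- That the share affected should be taken over all AEs starting in the 14-day window. That would include AEs still ongoing at first dose, whose end date does not contradict the imputed start.

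**Conclusion.** The point holds in a limited form. As written, cell (B) of SAP 2.9.1.6 assigns the day after first dose even when the recorded end date shows that the AE was already over, and SAP 2.1.1 then counts it as treatment-emergent. AEs with a complete start date, or with a partial one in an earlier month or year, are not misclassified.

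The 68% and 97% are shares of possible date patterns, not expected counts. They assume a 14-day pre-dose window, equal weight for each start/end pair, and first doses spread evenly over the assumed calendar range. The documents do not give the number of partial start dates, so the effect on this trial's tables cannot be sized and may be nil. This is a minor correction to a stated rule. It does not call the safety analysis as a whole into question.

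**What to change.** Add one sentence to SAP 2.9.1.6: when the AE end date is known to be before first dose, the imputed start may not be later than the end date, and the AE is classed as pre-treatment. In all other cases, including a missing end date or a partial end date that leaves the order open, keep the day after first dose.

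Next to the sentence on AE end dates in the same section, add a cross-reference to the duration-only exception in SAP 4.1, so that the two sections do not appear to conflict.

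The cost is a short SAP amendment and one programmed comparison, like the one SAP 2.5.1.1 already makes for dosing dates. No new data are needed.
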